5.1.2 Secondary Endpoints

- AEs and serious adverse events (SAEs), as well as changes in clinical laboratory values, vital sign measurements and ECG parameters
- Standard primary PK parameters, including, but not limited to, the area under the concentration-time curve from zero time to time of last quantifiable concentration (AUC_(0-t)), C_{max}, t_{max}, plasma concentration at 24 hours postdose (nominal sampling time point) (C₂₄), and ratio of the drug-drug interaction (DDI) effect
- ORR, defined as the proportion of subjects achieving a best overall response (BOR) of confirmed partial response or complete response (PR+CR)
- DOR, defined as the time from the date of the first documented and confirmed CR or PR until the first documentation of disease progression (PD) as determined by the investigator or death, whichever comes first. This is only defined for subjects with confirmed responses.
- CBR, defined as the proportion of subjects achieving a best overall response of confirmed partial or complete response, or durable SD (duration is at least 23 weeks). For subjects whose BOR is SD, duration of SD is defined as the time from the date of first dose to the date of the first documentation of disease progression or death, whichever occurs first. Note that for subjects without measurable lesion at baseline, timepoint response of Non-CR/non-PD will be considered as SD for analysis purpose
- PFS, defined as the time from the first dose date to the date of the first documentation of disease progression as determined by the investigator or death (whichever occurs first)
- OS, defined as the time from first dose date to the date of death from any cause.

Eisai Confidential Page 10 of 30

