5.3.5 Handling of Missing Data, Dropouts, and Outliers

Subjects that drop out and are unevaluable for DLT evaluation would be replaced per protocol.

No imputation for missing data will be performed in general, unless it is indicated for specific considerations. The imputation rules for partial date in order to derive a variable for disease characteristics will be specified in the study analysis dataset specification. For incomplete dates involving efficacy and safety data such as AEs, concomitant medications, laboratory values, vital signs and ECGs, a conservative imputation will be used for calculation. The imputation rules will be specified in study analysis dataset specification with more details. For endpoints that determine the percentage of responders, subjects with unknown response will be treated as non-responders.

Eisai Confidential Page 13 of 30

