5.4.2 Secondary Efficacy Analyses

ORR and CBR will be summarized by treatment groups, and exact 95% CIs will be provided using the method of Clopper and Pearson (1934).

In addition, waterfall plot of best percentage change of sum of diameters in target lesion will be provided for RES subjects

PFS analysis will follow the FDA censoring rule guidance: progression date is assigned to the earliest date when any RECIST 1.1-defined disease progression is observed without missing more than 1 adequate radiologic assessments. Details are included in Appendix 13.2. The distribution of PFS will be estimated using Kaplan-Meier methodology. Median PFS and the corresponding 2-sided 95% CIs (Brookmeyer and Crowley, 1982) will be summarized by treatment groups. The PFS rate at 3-month, 6-month, and 9-month and 12-month will be estimated using the Kaplan-Meier Method and the corresponding 2-sided 95% CIs will be summarized. In addition, Kaplan-Meier plots of PFS will be presented.

DOR will be calculated for subjects achieving a best overall response of confirmed PR+CR. If there are ≥7 subjects with confirmed responses, the median of DOR will be estimated using Kaplan-Meier methodology; median DOR and the corresponding 2-sided 95% CI will be presented by treatment groups on RES. The same logics in censoring rules as those for PFS analysis will be applied. If there are <7 subjects with confirmed responses, DOR will be listed.

OS will be censored at the last alive date or data cutoff date, whichever comes first. The distribution of OS will be estimated using Kaplan-Meier methodology. Median survival time and the corresponding 95% CI, survival rates at 6, 12, 18, 24 months, and corresponding 95% CIs will be estimated using Kaplan-Meier method. The analysis will be presented by treatment groups.

Eisai Confidential Page 14 of 30

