13 APPENDICES

13.1 General rules deriving best overall response (BOR)

The best overall response (BOR) is determined once all the data for the subject is known. For this study, a confirmation of complete responses or partial responses is required ≥4 weeks after the initial assessment of response. In order for SD to be considered the best overall response, it must occur ≥7 weeks following the first dose of study drug. For subjects who does not have target lesion at baseline, a timepoint response of Non-CR/Non-PD will be treated as SD in BOR derivation, and will be included in DCR and CBR calculation

To program the BOR per RECIST, the rules below will be followed:

- 1. The tumor response data collected via the CRFs will be used; and
- 2. Any further response assessments after the first PD identified will not be considered for the BOR determination, however they will be presented in the data listings; and
- 3. Any tumor assessments after the subject starts a new anti-cancer therapy will not be considered; and
- 4. If there are 2 or more consecutive missing adequate tumor assessments, all subsequent assessments will not be considered for the determination of BOR.

Note that the duration between 2 adequate tumor assessments, as well as the duration between the last adequate tumor assessment and death or PD, will be used to identify the cases where 2 or more consecutive tumor assessments are missing. Using the start day and the end day to denote the study days of the 2 endpoints of the duration, duration = end day – start day. If the duration is longer than 16 weeks +2x7 days (tumor assessment window) – 1 day (ie, 125 days), then it is considered that 2 or more consecutive adequate tumor assessments are missing.

Table 5 General Rules Deriving BOR per RECIST 1.1

Timepoint 1 Overall Response	Timepoint 2 (≥4 weeks since Timepoint 1) Overall Response	BOR ^b
CR	CR	CR
CR	PR	SD, PD or PR If a CR is truly met at first time point, then any disease seen at a subsequent time point, even disease meeting PR criteria relative to baseline, makes the disease PD at that point (since disease must have reappeared after CR). Best response would depend on whether minimum duration for SD was met. However, sometimes 'CR' may be claimed when subsequent scans suggest small lesions were likely still

Eisai Confidential Page 26 of 30

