		present and in fact the subject had PR, not CR at the first time point. Under these circumstances, the original CR should be changed to PR and the best response is PR.
CR	SD/PD	SD if duration of SD ≥7 weeks, otherwise PD
CR	NE	SD if duration of SD ≥7 weeks, otherwise NE. In a special case, if CR is at the next timepoint after NE, BOR will be CR.
CR ^a		SD if duration of SD ≥7 weeks, otherwise NE
PR	CR/PR	PR
PR	SD/PD	SD if duration of SD ≥7 weeks, otherwise PD
PR	NE	SD if duration of SD ≥7 weeks, otherwise NE. In a special case, if PR or CR is at the next timepoint after NE, BOR will be PR.
PR ^a		SD if duration of SD ≥7 weeks, otherwise NE
SD	Any response	SD if duration of SD ≥7 weeks, otherwise PD
PD		PD
NE		NE if the subject did not have a post-baseline tumor assessment, or if the subject only had one post-baseline tumor assessment of an early SD (duration <7 weeks) as the overall response, or post-baseline tumor assessments are not evaluable (ie, recorded as 'NE' as overall responses via the CRF)
UNK		UNK if the subject did not have a baseline tumor assessment

BOR = best overall response, CR = complete response, CRF = case report form, NE = not evaluable, PD = disease progression, PR = partial response, SD = stable disease, UNK = unknown.

13.2 **PFS Censoring rules**

For the main analysis of PFS, the censoring rules in this SAP and definition of progression date follow the principles of the FDA *Guidance for Industry: Clinical Trial Endpoints for the Approval of Cancer Drugs and Biologics* (2018). Table 6 below shows the censoring rules for the derivation of PFS.

Eisai Confidential Page 27 of 30

a: If this was the only tumor response assessment (eg, study treatment was discontinued).

b: For subjects who does not have target lesion at baseline, a timepoint response of Non-CR/Non-PD will be treated as SD in BOR derivation.

Table 6 Censoring Rules for the Derivation of PFS in Primary Analysis

No.	Situation	Date of Event (Progression/Death) or Censoring	Outcome
	No baseline or post-baseline tumor assessments	Date of first dose	Censored
2	Progression documented between scheduled visits	Date of first radiologic PD assessment	Event
3		Date of last adequate radiologic assessment prior to or on date of data cutoff	Censored
4	New anticancer treatment started	Date of last adequate radiologic assessment prior to or on date of new anticancer treatment	Censored
5	Death before first PD assessment	Date of death	Event

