6	Death between adequate assessment visits ^a	Date of death	Event
		Date of last adequate radiologic assessment before missed tumor assessments	Censored

CR = complete response, PD = disease progression, PFS = progression-free survival, PR = partial response, SD = stable disease.

The priority of the censoring rules is as follows:

- 1. If the subject had PD or death, the following sequence will be applied:
- If a subject did not have a baseline tumor assessment (No. 1), the subject will be censored on the date of first dose. If the subject died within 125 days following first dose and did not receive a new anticancer treatment, it will be counted as an event at the date of death. If a subject had new anticancer treatment before PD or death (No. 4), the subject will be censored on the date of the last adequate tumor assessment prior to or on the date of new anticancer treatment.
- If a subject missed 2 or more tumor assessments (>125 days) before PD or death (No. 7), the subject will be censored on the date of the last adequate tumor assessment before PD or death. Note that if a subject is censored by both this criterion and the anticancer treatment criterion, the earliest censoring date will be used.

Eisai Confidential Page 28 of 30

a: Adequate tumor assessment is radiological assessment of CR, PR, SD, non-CR/non-PD or PD as determined by investigators at regular interval as defined in the protocol. Any tumor assessments after new anticancer treatment starts will be removed in the definition of PFS.

b: Defined in Appendix 13.1.

- Otherwise, if a subject had an event (No. 2, No. 5, or No. 6), the earliest event date will be used.
- 2. If a subject did not have PD or death, the censoring date will be the earliest censoring date if the subject met multiple censoring criteria (No. 1, No. 3, No. 4 or No. 7).

Eisai Confidential Page 29 of 30

SIGNATURE PAGE

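### The stable-disease duration used for CBR lacks the PFS censoring rules, so a subject whom PFS censors at day 56 can count as 23-week clinical benefit

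*SAP*

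**What the plan says.** SAP 5.1.2 counts a subject toward CBR if her best overall response (BOR) is a confirmed PR or CR, or SD lasting at least 23 weeks. When stable disease is the best response, the rule reads "duration of SD is defined as the time from the date of first dose to the date of the first documentation of disease progression"; an earlier death also ends it. That section gives no other rule for the duration.

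PFS has the same start and end points in 5.1.2, but Appendix 13.2 adds three rules:

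- **New therapy:** the censoring date is "Date of last adequate radiologic assessment prior to or on date of new anticancer treatment".
- **Gap:** "If a subject missed 2 or more tumor assessments (>125 days) before PD or death (No. 7), the subject will be censored", at the last adequate assessment before the event.
- **No event:** "If a subject did not have PD or death, the censoring date will be the earliest censoring date" among those that apply.

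SAP 5.4.2 carries this over to DOR ("The same logics in censoring rules as those for PFS analysis will be applied") and gives OS its own censoring rule. It says nothing for SD duration.

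Two rules in Appendix 13.1 come close, but both concern the derivation of BOR. One deals with new therapy: "Any tumor assessments after the subject starts a new anti-cancer therapy will not be considered". The other deals with gaps in scanning: "If there are 2 or more consecutive missing adequate tumor assessments, all subsequent assessments will not be considered for the determination of BOR". SAP 5.3.5 adds: "For endpoints that determine the percentage of responders, subjects with unknown response will be treated as non-responders".

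**The concern.** Read as written, the SD clock stops only at documented progression or death. A subject can leave observation at week 8, or move to another anticancer drug, and the clock keeps running. If a late event is recorded, the whole interval counts as stable disease. Her CBR record then says 23 weeks of benefit, while her PFS record says that nothing is known after day 56. If no event is recorded, the duration does not exist, and the programmer must choose an end date.

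CBR is one of the five activity measures named in the secondary objectives. It is reported by treatment group with exact confidence intervals, in planned cohorts of 6. SAP 3.2 states that no expansion subjects will be enrolled, so these small groups supply all the activity data.

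**Working it through.** **Inputs.** Days are counted from first dose.

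- Durable SD (SAP 5.1.2): 23 × 7 = 161 days.
- Scans every 8 weeks ± 7 days (Protocol 9.6.1.2.1, SAP 3.2): week-8 window days 49–63, week-24 window days 161–175.
- Earliest SD that can be a BOR (Appendix 13.1): 7 × 7 = 49 days.
- Gap limit (Appendix 13.1): 16 × 7 + 2 × 7 − 1 = 125 days. This reproduces the SAP's own figure.
- Cutoff about 6 months after the last subject's first dose (SAP 3.2): 6 × 30.4375 = 182.6 days, using the month length in SAP 5.6.1.
- Cohort size 6 (Protocol 9.1, Table 3).

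**Both definitions applied to the same constructed subjects.** The last SD scan is on day 56 except in the final row.

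| Course | SD duration, SAP 5.1.2 | Counts in CBR? | PFS, Appendix 13.2 |
|---|---|---|---|
| New therapy day 60, death day 170 | 170/7 = 24.3 weeks | Yes | Censored day 56; gap 170 − 56 = 114, so only the new-therapy rule acts |
| New therapy week 10, death day 210 | 210/7 = 30.0 weeks | Yes | Censored day 56; gap 210 − 56 = 154, so both rules act |
| PD first found day 190 | 190/7 = 27.1 weeks | Yes | Censored day 56; gap 190 − 56 = 134 |
| Death day 181 | 181/7 = 25.9 weeks | Yes | Event day 181; gap exactly 125, no conflict |
| Lost after day 56, no event | Undefined | Not settled | Censored day 56 |
| SD at day-168 scan, no event | Undefined | Not settled | Censored day 168 |

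**When each route operates.**

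- *New therapy.* Scheduled scans stop at new therapy (Protocol 9.1.3), so in practice this route needs a death on or after day 161. Survival follow-up, about every 3 months until cutoff, records such deaths.
- *Gap.* PFS censors only if the event falls more than 125 days after the last adequate scan. For last scans on days 49, 56 and 63 that means after days 174, 181 and 188. All three exceed 161, so any subject with a qualifying SD scan whom PFS censors by the gap rule before PD or death counts as benefit on the literal text. The last subject's cutoff is near day 183, so this route mainly concerns subjects enrolled earlier.
- *No event.* The choice of end date matters mainly for subjects last scanned before day 161: they fail if the clock stops at the last scan, but could pass if it stops at cutoff. Read strictly, subjects with SD at week 24 and no event also lack a duration.

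**Size.** One subject in a cohort of 6 is 1/6 = 16.7 points. With an illustrative base of 2/6, CBR goes from 33.3% (Clopper-Pearson 95% CI 4.3 to 77.7) to 3/6 = 50.0% (11.8 to 88.2). If only 5 or 4 of a cohort had measurable disease and entered the Response-Evaluable Set (an assumption), one subject is 1/5 = 20.0 or 1/4 = 25.0 points.

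**The case against.** The strongest reply is that the PFS rules are implied. SD duration and PFS share their definition in 5.1.2, where PFS carries no censoring text either. CBR is built on BOR, and Appendix 13.1, which mentions CBR, contains both a new-therapy and a gap rule. Its Table 5 also treats a single early SD scan as having a duration below 7 weeks, which makes sense only if duration is measured to the scan.

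Part of this stands. The SAP uses SD duration in two senses, and the authors may well have intended a PFS-type derivation. If the BOR gap rule were also read as removing the day-190 progression, that example would no longer give 27.1 weeks. But the duration would then run to death or be undefined; it would not stop at day 56. A death is not a tumor assessment, so neither BOR rule removes the day-170 death. The extension to DOR had to be stated, and none is stated here. The rule for unknown response does not clearly apply either, because this subject's BOR is SD.

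It is also fair that the separate programming documents (SAP 9) may hold a rule, that the two intervals above overlap heavily, and that each route needs an uncommon sequence of events. These points limit the consequence but do not supply the missing rule.

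**Conclusion.** The concern holds. On the SAP text, a subject whose last evidence of stable disease is at week 8 can be reported as having 23-week benefit while PFS censors her at day 56, and event-free SD subjects have no defined duration. Each affected subject is worth 16.7 points in a cohort of 6.

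The subjects above are constructed. The number affected and the net direction are unknown: the first two routes inflate CBR, and the no-event branch could go either way. The conclusion rests on the SAP text alone. Because CBR is descriptive and the MTD/RP2D does not depend on this calculation, this should be corrected but does not threaten the primary objective.

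**What to change.** In SAP 5.1.2, keep PD or death as the end date and add:

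> For CBR, duration of SD follows the Appendix 13.2 rules for PFS. It ends at PD or death if that is a PFS event. Otherwise it ends at the last adequate tumor assessment before new anticancer therapy, before a gap of more than 125 days, or, without PD or death, on or before data cutoff. Durable SD requires a duration of at least 161 days; otherwise the subject is not counted as clinical benefit.

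This reuses the PFS derivation and data already collected. Reported CBR may be slightly lower. An event-free subject last scanned before day 161, for example after a missed or early week-24 scan, would not qualify, although one who progresses on day 168 without a gap would. An in-window week-24 scan showing SD is enough. An event on days 161–181 after a last scan on day 56 would still count, but CBR and PFS would then agree.

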5.1.3 Exploratory Endpoint

Not applicable.

5.2 Study Subjects

5.2.1 Definitions of Analysis Sets

- Safety Analysis Set: all subjects who receive at least 1 dose of study drug (either H3B-6545 or palbociclib, or both). This will be the analysis set for all safety evaluations except DLT results.
- Full Analysis Set (FAS): consists of all subjects who receive at least 1 dose of study drug.
- **Dose Evaluable Set**: consists of all subjects who were evaluable for DLT in dose escalation part (Phase 1b). This will be the analysis set for DLT results.
- Response-Evaluable Set (RES): consists of those subjects who receive at least 1 dose of study drug and have measurable disease at baseline and at least 1 adequate post-baseline tumor assessment. This will be the primary analysis set for efficacy evaluations of response rate.
- Pharmacokinetic Analysis Set: consists of subjects who received at least 1 dose of study drug and all valid plasma concentrations (at least 3 valid concentrations for noncompartmental analysis).

5.2.2 Subject Disposition

The number and percentage of subjects enrolled (ie, those who signed informed consent) along with reason for screen failure will be summarized.

The number of subjects in each analysis set will be summarized. The number and percentage (based on FAS) of subjects who completed/discontinued treatment will be summarized by treatment groups, along with the primary reason for discontinuation.

5.2.3 Protocol Deviations

All important protocol deviations will be determined prior to database lock and will be agreed upon by a cross-functional team review of individual subject data. The summary table and listing of important protocol deviations will be provided using data in the clinical database.

5.2.4 Demographic and Other Baseline Characteristics

Demographic and baseline characteristics for the FAS will be summarized by treatment groups using descriptive statistics. Continuous demographic and baseline variables will include age (year), weight (kg) and height (cm); categorical variables will include age group (≥ 18 to <65, ≥ 65) sex (male, female), race (White, Black or African American, Asian

Eisai Confidential Page 11 of 30

[Japanese, Chinese, Other Asian], American Indian or Alaska Native, Native Hawaiian or other Pacific Islander, and Other), Ethnicity (Hispanic or Latino, Not Hispanic or Latino), as well as the Eastern Cooperative Oncology Group Performance Status (ECOG PS), measurable disease at baseline, and bone disease without measurable lesion at baseline (defined by subjects without measurable disease and with non-target bone lesion presented at baseline).

Disease history will be summarized by treatment group:

- Time from tumor initial diagnosis to date of the first dose (months)
- Age at diagnosis (years) summarized both descriptively and by categories ($<65, \ge65$)

Disease characteristics at study entry will be summarized by treatment groups (based on FAS):

- Metastatic sites at baseline
- Mutation status of ESR1, PIK3CA, AKT1 at baseline
- Progesterone Receptor (PgR) status and positivity as percentage of PgR positive cells (per immunohistochemistry [IHC]) at baseline.

Previous anti-cancer medications will be summarized by treatment groups (based on FAS):

- Number of previous anti-cancer regimens containing endocrine therapies in locally advanced/metastatic disease settings
- Number of previous anti-cancer regimens not containing endocrine therapies in locally advanced/metastatic disease settings
- Therapeutic setting of previous anti-cancer regimens
- Type of previous anti-cancer regimens (endocrine, including fulvestrant, aromatase inhibitor, tamoxifen and other, CDK4/6 inhibitor, chemotherapy, other; CDK4/6i and AI; CDK4/6i and fulvestrant) in locally advanced/metastatic disease settings

Listings of demographics, baseline characteristics, disease history and characteristics, previous anti-cancer medications and previous radiotherapy will be provided.

Medical history and current medical condition

Medical history and current medical condition, as recorded on the case report form (CRF), will be listed. Reported medical conditions will be coded using Medical Dictionary for Regulatory Activities (MedDRA), version 19.0 or later.

5.2.5 Prior and Concomitant Therapy

All investigator terms for medications recorded in the CRF will be coded to an 11-digit code using current version of the World Health Organization Drug Dictionary (WHODD).

Eisai Confidential Page 12 of 30

Prior medications will be defined as medications that started before the first dose of study drug. Concomitant medications will be defined as medications taken during the treatment period (defined as the period from first dose date to 28 days after last dose date).

Note that a medication can be categorized into multiple categories: it can be prior only, concomitant only, or combination of prior and concomitant.

The number (percentage) of subjects who took prior and concomitant medications will be summarized on the FAS by treatment groups and by Anatomical Therapeutic Chemical (ATC) class (level 1 and level 3), as well as WHO DD preferred term (PT). All medications will be presented in subject data listings.

